Duration of Intervention: Implementing a dietary intervention can present some challenges with regard to dietary compliance as well as subject retention for the duration of a study. Our preliminary data shows a significant effect of low carbohydrate diet after 9 weeks of intervention – all subjects with GERD had resolution of their symptoms and GERD medication use. In the proposed study, we have chosen to continue to use a 9-week intervention period as we would expect that obese adults may find it difficult to adhere to a longer term dietary change and this study is not designed to investigate behavioral issues. Attrition would be problematic as it may statistically underpower the study or bias the results and negatively affect internal validity of the study. Our aim is to minimize potential attrition, maximize statistical power, and minimize the time commitment while providing a dietary intervention of adequate duration to experience effects.

Weight Loss: We recognize the benefits of weight loss in the obese veteran and are highly encouraged by the enormous resources dedicated to the MOVE! program. Interestingly, our preliminary data showed resolution of GERD symptoms and medication use, as well as improvement in insulin sensitivity – independent of weight loss. To clearly determine the effects of the modifying dietary carbohydrate intake *per se* and control for potential confounding (which would distort study findings) by changes in body weight during the course of the study, subjects will be prescribed diets in which the energy content will maintain body weight, not induce weight loss. Body weight will be monitored by the study dietitian. Body composition will be assessed at end of study weeks 1 and 9 by use of DEXA (described in Measures section below). Upon completion, the study dietitian will counsel subjects about unhealthy weight and provide a written handout on caloric reduction for weight loss.

2.2 Methods:

Design: Randomized controlled dietary trial with 4 treatment arms comparing amount and type of CHO:

- High total & high simple carbohydrate (HTHS): 50% complex CHO + 50% simple CHO (control diet)
- High total & low simple carbohydrate (HTLS): 85% complex CHO + 15% simple CHO
- Low total & high simple carbohydrate (LTHS): 50% complex CHO + 50% simple CHO
- Low total & low simple carbohydrate (LTLS): 85% complex CHO + 15% simple CHO

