A secondary recruitment strategy will involve the placement of IRB approved posters and brochures in the waiting areas of target clinics with basic study information and a contact line for potential subjects to register potential interest. We anticipate screening 6-10 subjects per week for eligibility. We will perform a baseline pH study after consent. Based on clinical experience, we expect 15-20% of Vets diagnosed with GERD will be screen failures as they will not have pH < 4.0 for > 5.5% of a 24-hour period (personal communications [name] & [name]). These 15-20% will be excluded from study as the underlying hypothesis is that low carbohydrate / low sugar diet will reduce % time with pH < 4.0 to < 5.5%. Thus, we expect to meet our targeted enrollment of 1-2 subjects per week, which is based on the ability to schedule this number of patients in the GI clinic for pH testing. Thus, our recruitment and enrollment goals appear to be highly feasible with such a huge patient population at TVHS (currently a total of 65,000 patients; 29,250 of whom are obese, and 19,100 are currently on PPIs, thus ~65% of these obese vets have GERD).

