6.0 Study Procedures

Randomization: 200 subjects (50 per arm) will be randomized to diet treatment arm. we have reviewed drop-out rate from clinical trials in gastroenterology in this population ([name] and [name] personal communications), which would predict a 20% drop out rate. The number of subjects to enroll reflects a completion rate of 80% (enroll 50 per arm = 200 subjects x 0.80 = 160 completers). In considering that drop out could be higher, we will now include subjects in our final analyses who notify us they are dropping-out between weeks 7-9 by asking them to return for a final visit at the time of drop-out (we do this regularly and get agreement from about 66% of subjects to return for a final testing session even if they are not continuing to wk 9). Randomization of subjects will be carried out using unified reproducible methods (i.e. saved random number seed) provided by the Biostatistician ([name]). We will use a permuted block randomization scheme, stratifying on gender to ensure this covariate is balanced

between randomization groups. The block size will be varied randomly. Treatment assignments will be contained in sealed, thick envelopes to be opened after informed consent is obtained.

Overall Schema:

Timepoint	Baseline	Day 1-7	End Wk 1	Day 8-57	Day 57-63	End Wk 9
Consent & Enrollment	X					
Randomization			X			
Bloodwork	X		X		X	X
Diet Intervention						
Off PPIs #1						
Clinical Testing #1				X		
Off PPIs #2						
Clinical Testing #2						X

Testing Procedures:

Baseline levels of all measures listed below will be obtained prior to study day 1.

PPIs will be stopped for 1 week, medications that affect gastric motility for 2 days, H₂RAs for 2 days, and antacids for 2 days - *prior to testing on study days 7 and 63. Additional blood work will be drawn on study day 57 for evaluation of levels prior to discontinuation of PPIs #2.*

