Subjects will be instructed to stop eating and drinking, except water, at 10pm on the evening before each clinical testing day. Thus, subjects will arrive at the VA on study days 7 and 63 NPO. Subjects will be escorted by study staff from the VA to the Vanderbilt Clinical Research Center at 0700. Subjects will be admitted to a private outpatient room (has private bed and bathroom). An updated medical history will be obtained to ensure absence of recent/current illness. CRC nursing will obtain vital signs and perform the blood draw. As part of the blood draw, female subjects will have a pregnancy test (via serum βHCG). The study dietitian will perform anthropometric, body composition (DEXA), dietary and GERD symptom survey measures as described below. The subject will then be escorted by study nurse to the Vanderbilt GI Clinic for impedance monitoring and gastric emptying test procedures under the guidance of [name] (study co-investigator), as described below. Impedance monitoring will continue for a 24-hour period. Subjects will be provided with a meal that is consistent with the diet intervention and the treatment arm they are assigned to before being discharged home. The study nurse will telephone subjects in the early evening to assure no problems from study procedures have developed. Subjects will return to the VA to meet briefly with the study nurse on the day after clinical testing to allow data retrieval and return of impedance monitoring and gastric emptying equipment.

For these Testing Visits, at the end of study week 1 and study week 9, participants have the choice of staying overnight in a private room at the Vanderbilt Clinical Research Center for the 24-hour period of testing, or they can return to the Vanderbilt Digestive Disease clinic on the morning after the 24-hours of pH and SmartPill monitoring for the removal of the pH catheter and collection of the recording devices.

Measures: to be performed in the fasting state at baseline, end study week 1, pre/post study week 9

- **Bloodwork:**
 - **Glucose:** Plasma glucose concentration will be analyzed in triplicate via glucose oxidase method using a Beckman glucose analyzer at the VA Clinical Laboratory.
 - **Insulin:** Plasma insulin concentration will be shipped to LabCorp and analyzed by radioimmunoassay method.
 - **HOMA-IR:** Calculated from glucose and insulin values.

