 - **Hormones:** Serum gastrin will be assayed at LabCorp. Glucagon and GLP-1 by Luminex multiplex assay at the Diabetes Hormone core lab. Serum ghrelin (active acylated form) by radioimmunoassay at the Diabetes Hormone core lab. While several other hormones are involved in gastric acid secretion and motility, we have chosen two key stimulators (gastrin and glucagon) and two key inhibitors (GLP-1 and ghrelin), as well as insulin, to investigate in this proposal utilizing a dietary intervention in obesity.
- **Anthropometrics:**
 - **Height** (m) and **Weight** (kg) measured on calibrated digital equipment will be used to calculate **BMI**.
 - **Waist Circumference** will be measured using a flexible tape at the level of the umbilicus.⁴⁵
- **Body Composition:** In addition to total and regional body composition (fat, lean and bone mass) obtained from the Lunar iDXA (GE Healthcare), we will use new technology recently acquired by VICTR to estimate visceral adipose tissue (VAT) – a possible risk factor for GERD.⁴⁶ This fully automated approach to capture VAT has been validated against CT⁴⁷ and offers several advantages to MRI or CT: fast, low cost, exposes one to less radiation, and makes serial measurements possible.
- **Metabolic Testing:** To capture a more objective measure of change in energy balance due to the dietary intervention, we will perform indirect calorimetry by metabolic cart while subjects are at the CRC on week 1 and 9.
- **24 hour urine collection:** To effectively measure how well the body processes food intake
- **Dietary Intake:** will be assessed via averaging three 24-hour diet recalls obtained at baseline and again within a 7-day window of each clinical testing visit (study weeks 1 and 9). Recalls will be performed by the Vanderbilt Nutrition and Diet Assessment Core using the USDA multi-pass methodology,^{48,49} a standardized script, and computer-generated prompts (NDS-R, v. 2013, Nutrition Coordinating Center, Minn, MN). We are familiar with underreporting especially in people with high BMI and use portion size tools and statistical methods to assure

data reliability. The 1st of 3 recalls will be in-person at the CRC, which allows training of subjects in the interview methodology.

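### The plan conflicts on which pre-diet 24-hour pH recording is the baseline, and does not say that the randomisation envelope stays closed until the 5.5% entry result is known

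*Combined protocol and SAP*

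**What the plan says.** The entry rule in section 4.0 excludes anyone whose baseline 24-hour test does not reach the 5.5% threshold. The model in section 10.0 sets t=0 at baseline, with one mean shared by all arms. Neither section ties the word baseline to a study day.

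Several places put the baseline before week 1:
- Section 5.0: "We will perform a baseline pH study after consent", and of those who do not meet the threshold, "we expect 15-20% of Vets diagnosed with GERD will be screen failures".
- Section 6.0, Testing Procedures: "Baseline levels of all measures listed below will be obtained prior to study day 1". The measures listed below that sentence include 24-hour impedance monitoring.
- Section 6.0, Measures: "to be performed in the fasting state at baseline, end study week 1, pre/post study week 9", so baseline and end of week 1 are separate occasions.
- Section 6.0, Dietary Intake: recalls are "obtained at baseline and again within a 7-day window of each clinical testing visit (study weeks 1 and 9").

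Other places point to day 7:
- Section 6.0 stops PPIs, H2RAs, antacids and motility drugs "prior to testing on study days 7 and 63". No other stop is scheduled.
- Section 2.1: "Body composition will be assessed at end of study weeks 1 and 9 by use of DEXA". Section 7.0 likewise counts two scans.
- The section 10.0 model has two outcome times per subject.

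On assignment, section 6.0 says the envelopes are opened once consent has been given, and names no other condition. The schema marks Randomization at the end of week 1. Section 2.2 has the dietitian teach the arm's meal plan at the end of week 1. The test-day procedure, written for days 7 and 63 alike, says subjects are "provided with a meal that is consistent with the diet intervention and the treatment arm they are assigned to before being discharged home".

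**The concern.** The primary outcome depends on one pre-diet measurement, which also serves as the entry test unless the two are meant to be separate recordings. If day 7 is used for either purpose, the written procedure has two consequences.

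First, a meal chosen by arm falls inside the recording of subjects who go home the same day. The t=0 value is then taken partly after treatment, and the model's single baseline mean need not hold.

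Second, serving that meal requires the arm to be known before the 24-hour tracing is complete and manually reviewed. Passing or failing the 5.5% test could then depend on the arm, and a failure would be an exclusion after randomisation. Analysis cannot fully repair exclusions that depend on assignment.

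**Working it through.** **1. Side by side.**

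| Question | Baseline before day 1 | Baseline on day 7 |
|---|---|---|
| Off PPIs? | Possible: section 2.1 has a general 7-day rule before impedance testing, with no visit named | Yes, scheduled in section 6.0 |
| Fits the statement that all baseline measures precede day 1? | Yes | No |
| Fits the two-time model? | Yes, but the day-7 recording then has no stated role | Yes |
| Entry result known before randomisation at end of week 1? | Yes, if the schema is followed | No: the recording starts at that visit and runs 24 hours |
| Arm-specific meal inside the recording? | No | Yes for same-day discharge; for overnight stayers it could come after |

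Neither column fits every sentence. A third arrangement is also possible: an entry test before day 1, with day 7 as t=0. Only the meal problem then remains. Table columns may have shifted when the PDF was converted, so the schema's marks carry limited weight.

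**2. The plan's own figures.** Section 6.0: 200 × 0.80 = 160 completers, which reproduces. For power I used the section 10.0 model by generalised least squares, a noncentral F test with N−4 denominator d.f., ICC 0.39, and per group 40 completers plus 5 early leavers at t=0.8. Taking 9.8 as the residual SD, the 4-d.f. powers are 0.80, 0.89, 0.79, 0.85 and 0.87, against the stated 0.80, 0.89, 0.80, 0.85 and 0.87. Taking 9.8 as the total SD gives 0.96 to 0.99, which does not match the table.

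**3. If pH failures occur before randomisation.** Randomised and completer numbers stand at 200 and 160. The number to consent and test is 200/0.85 = 235.3, so 236, up to 200/0.80 = 250.

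**4. If pH failures were removed after randomisation.**
- 15% fail: 200 × 0.85 × 0.80 = 136 completers, 34 per arm.
- 20% fail: 200 × 0.80 × 0.80 = 128 completers, 32 per arm.
- With early leavers scaled to 4 per arm, 4-d.f. power over the five scenarios is 0.68 to 0.82 with 9.8 as residual SD, or 0.90 to 0.97 with 9.8 as total SD.

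**5. If an arm-specific meal fell inside t=0.** Let f be the share of the diet effect already present in that recording. The documents give no value, so 0.05 to 0.10 is an assumption. With a common baseline mean, the model estimates a between-arm contrast as the follow-up difference minus ICC times the baseline difference. The share retained is therefore 1 − 0.39f (exact when t=1):
- f = 0.05: 1 − 0.0195 = 0.98
- f = 0.10: 1 − 0.039 = 0.96

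The contrast shrinks by about 2% to 4%. A meal that shifted acid exposure the other way would inflate it by the same amount. With residual SD 9.8, the 4-d.f. power range moves from 0.79-0.89 to 0.75-0.86 at f = 0.05 and 0.70-0.83 at f = 0.10. The between-arm 3-d.f. test loses about 1 to 4 points. These figures illustrate sensitivity; they do not estimate what will happen.

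**The case against.** A fair defence is that the sequence can be inferred. Consent comes first, then a baseline pH study, and failures are called screen failures and excluded. The schema puts consent at baseline and randomisation about a week later. The statement about consent sets an earliest time for opening the envelope, not the only condition. The general 7-day rule would make a recording before day 1 off-PPI. On that reading, no arm-specific meal touches the baseline and no exclusion follows assignment. The DEXA count concerns body composition rather than pH, and the two-time model fits either reading. The day-7 case therefore rests mainly on the washout sentence and the meal sentence.

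Most of this stands, and it limits the point. A reader might infer three stronger claims that the documents do not support:

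- *That the plan has no off-PPI recording before day 1.* Sections 2.1 and 6.0 together can describe one.
- *That ineligible subjects will be randomised and the trial left underpowered.* The term screen failures points the other way. The plan only fails to rule it out.
- *That one recording must be both entry test and t=0.* Separate recordings are legitimate, and sharing one has a cost. If values are normal, 9.8 is the total SD and the lowest 15-20% are cut, selected subjects start above the population mean by 9.8 × 0.274 to 9.8 × 0.350. The expected fall with no diet effect is 0.61 times that, about 1.6 to 2.1 points in every arm. The 4-d.f. test counts this fall; between-arm contrasts do not.

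The defence does not remove the conflict itself. Drug stops are scheduled for days 7 and 63 only, and the meal sentence covers day 7. With randomisation at the end of week 1, following the text on day 7 puts the arm in use before that day's result exists.

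**Conclusion.** The conflict over which recording is the baseline is in the text, and so is the missing rule linking the envelope to the entry result. The consequence is conditional. If day 7 supplies the entry test or t=0, the baseline value and the 5.5% exclusions could depend on the assigned arm. If a washed-out recording before day 1 supplies both, they could not, and what is missing is a stated role for the day-7 recording.

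The size and direction of any bias are unknown, because f has no source in the documents. The fall to 128-136 completers requires removal after randomisation, which the plan's wording speaks against. No power loss should be claimed as established. Confidence is medium. This is a cheap improvement, worth making because it protects the entry criterion and the t=0 value at little cost.

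**What to change.** 1. State in sections 4.0, 5.0, 6.0 and 10.0 which recording is the 5.5% entry test and which is t=0. They may be the same or different. Show each with its washout in the schema. If the day-7 recording is neither, say how it is used.
2. Open the envelope only after the entry tracing has been reviewed and the 5.5% criterion confirmed. Count the 200 from that point.
3. Reconcile the meal sentence in section 6.0 with the randomisation and diet-instruction timing in sections 2.2 and 6.0, so that nothing arm-specific falls inside a recording used as entry test or t=0. The choice of meal and diet schedule stays with the investigators.

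The cost is mostly wording. If day 7 is the entry test or t=0, diet start moves by about a day, or longer if manual review takes longer, and a dietitian slot is needed at the existing next-day return. If a recording before day 1 is meant, it needs its own schema row with its washout.

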- HTLS Diet: 55% total CHO (85% complex / 15% simple CHO), 30% fat, 15% protein
- LTHS Diet: 35% total CHO (½ complex / ½ simple CHO), 50% fat, 15% protein
- LTLS Diet: 35% total CHO (85% complex / 15% simple CHO), 50% fat, 15% protein

Power Analysis and Sample Size: Our primary outcome is a continuous variable, percent time pH < 4.0 in the 24hr period. This is based on the clinical gold standard of pH < 4.0 for > 5.5% of the 24hr period. To determine sample size, we used data from 205 obese patients with chronic GERD from [name] clinic population. In this sample, the SD for percent time < pH was 9.8 and the interclass correlation was 0.39 ($\omega = \omega^2_b / (\omega^2_b + \omega^2_e)$). We used these values as inputs into a statistical simulation (10,000 replications) to determine the probability of detecting any treatment group effect using the linear mixed effects model. The following table presents the power of an overall (4 d.f.) test to detect various absolute changes in pH by diet groups ($\omega_1, \omega_2, \omega_3, \omega_4$). We assume $n_1=40$ subjects per group complete the entire study and $n_2=5$ or $n_2=3$ subjects per group complete 80% of the study before returning for pH testing. We use a two-sided significance level of 0.05.

Absolute effect size	3.7%, 3.7%, 3.7%, 3.7%	0%, 4.5%, 4.5%, 4.5%	0%, 4%, 4%, 4%	0%, 0%, 5%, 5%	0%, 0%, 0%, 7%
Power ($n_1=40, n_2=5$)	0.80	0.89	0.80	0.85	0.87
Power ($n_1=40, n_2=3$)	0.79	0.88	0.79	0.83	0.86

Power for different effect size scenarios that give 80%-90% power are presented in the table. If the absolute change in percent time pH < 4 for each of the four diet groups is 3.7%, we will have 80% power to detect any effect of diet. If 1 diet group is not effective and the other groups have a 4.5% effect, we have almost 90% power to detect a diet effect. In our pilot data, the 25th/50th/75th percentiles of percent time pH < 4 were 4.8%/8.5%/12.4%. Thus, a 3.7% decrease is a change from the median to 25th percentile, a 4% decrease is a change from the 75th percentile to the median, a 5% decrease is a change from the 80th percentile to the median, and a 7.6% decrease is a change from the 75th to the 25th percentile. The standard error for any pairwise comparison between groups will be 1.9% under all scenarios ($n_1=40$ and $n_2=3$ or $n_2=5$).

2.3 SPECIFIC AIMS:

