- **Medication Use:** will be assessed by two methods: a) we will provide subjects with a notebook that includes daily logs for them to record medication type and amount; and b) weekly interview by study nurse. In addition, we now have bloodwork being drawn pre and post weeks 1 and 9 that will inform medication use by measurement of hormone levels, i.e., gastrin.
- **24-Hour Impedance Monitoring:** will be performed by using a combined MII-pH monitoring device (Sandhill Scientific Inc; Highlands Ranch, CO) comprising a data recorder (Sleuth System; Sandhill Scientific Inc) and a 2.1 mm diameter polyvinyl catheter embedded by one pH and 6 impedance sensors at predefined positions. The pH sensors are calibrated before placement using standardized buffer solutions at pH 4.0 and 7.0 per manufacturer. The catheter is placed intranasally so that the esophageal pH sensor is positioned 5-cm above the manometrically defined upper border of the lower esophageal sphincter (LES). Intraluminal impedance is measured at 3, 5, 7, 9, 15 and 17cm above the LES. Data sampling frequency for both impedance and pH sensors is 50 Hz. Data are downloaded from the recorder and analyzed using BioView Analysis software (Sandhill Scientific Inc). Reflux episodes are identified by computerized detection (Autoscan; Sandhill Scientific Inc.) of proximally directed decreases in impedance. Tracings are also manually reviewed by an experienced investigator ([name]) to confirm accuracy and correct errors. Total, upright and supine reflux events are recorded. Acid reflux events are defined as those with pH \leq 4 and non- or weakly acid reflux events are those occurring at pH $>$ 4.

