11.0 Privacy/Confidentiality Issues

All efforts, within reason, will be made to keep personal information in the participant's research record confidential. Careful safeguards are in place, and confidentiality will be maintained by coding data and blood samples using only a number to identify the data. The number assigned will be specific to this study and will not be related to other personal identifiers such as medical record number, telephone number, social security number or initials. The identification number will only be known to the study staff. The record linking the study number with the participant's name will be maintained by [name], [name] and the study team. It will be kept in a locked research office and in a locked file cabinet. Computer data will be password-protected.

The Sponsor and/or Vanderbilt may share the participant's information, without identifiers, to others or use it for other research projects not listed in this form. The Sponsor, Vanderbilt, [name], [name] and the study team will comply with any

and all laws regarding the privacy of such information. There are no plans to pay the participant for the use or transfer of this de-identified information.

In compliance with the National Institute of Health data sharing initiative, imaging data without any personal information attached may be shared with other investigators or public data repositories, which provides the research community with open access to datasets contributed by labs around the world. Information will be completely anonymized with demographics limited to age (accurate to the year up to 90 years old, or "90+" for older individuals), gender (male, female), group membership (e.g., disease/treatment state) and handedness. Data will be transferred using secure file transfer protocols.

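### A study investigator may correct the pH-impedance tracings in an open-diet trial, and the plan does not mask that reader to arm or visit; reflux-episode counts are directly exposed, percent time pH < 4.0 possibly so.

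*Combined protocol and SAP*

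**What the plan says.** Section 6.0 (24-Hour Impedance Monitoring) describes a software reading followed by a human one. First, "Data are downloaded from the recorder and analyzed using BioView Analysis software", and "Reflux episodes are identified by computerized detection" of impedance changes. Then "Tracings are also manually reviewed by an experienced investigator", "to confirm accuracy and correct errors". The section gives no rule for what counts as an error, no second reader and no instruction to keep the automated result.

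Section 2.2 (Power Analysis and Sample Size) names the primary outcome: "Our primary outcome is a continuous variable, percent time pH < 4.0 in the 24hr period". It comes from the same combined recording. Aim 1 in Section 2.3 adds the number of reflux episodes as an outcome.

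Three other places bear on who knows what:

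- **Randomization, Section 6.0:** "Treatment assignments will be contained in sealed, thick envelopes to be opened after informed consent is obtained". This hides the next assignment; it does not hide assignments already made.
- **Diets, Section 2.2, and testing procedures, Section 6.0:** the dietitian teaches arm-specific meal plans, and at the testing visit "Subjects will be provided with a meal that is consistent with the diet intervention and the treatment arm they are assigned to". Some study staff therefore know the arm.
- **Section 11.0:** "confidentiality will be maintained by coding data and blood samples using only a number to identify the data". The same section says that study staff know the identification number and that the study team keeps the link to names.

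**The concern.** When a person may alter a reading by judgement and could know which diet the participant followed, or whether the tracing is the first or the last, small decisions about artefacts and doubtful episodes can lean one way. The protocol states a strong expectation: Section 1.0 reports that GERD symptoms resolved in every affected pilot participant, and the Interpretation part of Section 10.0 singles out simple carbohydrate as the factor most strongly linked to resolution. A lean of that kind is systematic, so more participants do not dilute it.

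Knowledge of visit matters as well as knowledge of arm. The model in Section 10.0 has one common baseline mean and a separate change for each of the four arms. The powered 4 d.f. test asks whether any of those changes differs from zero. A reader who knew only that a tracing was the final one, and read it a little more favourably in every arm, could move that test.

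**Working it through.** **1. Which outcomes can the reader reach?** In Section 6.0 the manual-review sentence comes directly after the software detection of impedance-defined episodes, and the next sentence concerns the recording of reflux events. Episode counts are therefore plainly within reach. Percent time pH < 4.0 comes from a calibrated sensor and software. A reader could change it, for example by excluding a stretch of record as artefact, but the protocol does not say whether this is allowed.

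**2. Inputs for a size check (Section 2.2).** SD 9.8; intraclass correlation 0.39; 40 completers per arm at t = 1 plus 5 per arm at t = 0.8; two-sided 0.05; stated pairwise SE 1.9. The bias itself is not in the documents, so shifts of 0.5, 1 and 2 points are assumed. One point is 0.01 × 24 × 60 = 14.4 minutes of recording. The documents give no SD for episode counts, so the effect on those cannot be sized.

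**3. Reproducing the plan's figure.** I used the Section 10.0 model (random intercept, common baseline, four arm-by-time effects) and generalized least squares. Each arm effect then has variance v, and each pair of effects has covariance c.

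- *9.8 as residual SD:* σ²e = 96.04; σ²b = 96.04 × 0.39/0.61 = 61.40; v = 3.427, c = 0.337. Pairwise SE = √[2(v − c)] = 2.49. For 3.7 points in all arms, λ = 3.7² × 4/(v + 3c) = 13.69 × 0.901 = 12.34, and power is 0.815 (plan: 0.80). All ten cells of the table reproduce within 2 points.
- *9.8 as total SD:* σ²b = 37.46; σ²e = 58.58; v = 2.091, c = 0.206. Pairwise SE = 1.94 (plan: 1.9), but λ = 13.69 × 1.477 = 20.23 and power is 0.966.

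The plan's power table fits the first reading and its SE fits the second. I therefore give each result as a range from SE 2.49 to SE 1.94.

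**4. True type I error under an assumed shift of b points.**

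- (a) Shift between two arms, pairwise test: Φ(−1.96 − b/SE) + 1 − Φ(1.96 − b/SE).
- (b) Same shift at the final visit in all four arms, 4 d.f. test: P(χ²₄(λ) > 9.49), λ = 4b²/(v + 3c).
- (c) Shift in the two low-simple arms only, 4 d.f. test: λ = b²[1/(v + 3c) + 1/(v − c)].

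| Assumed b | (a) pairwise | (b) all arms, final visit | (c) low-simple arms |
|---|---|---|---|
| 0.5 point | 5.5-5.8% | 6.1-6.9% | 5.7-6.1% |
| 1 point | 6.9-8.1% | 9.9-13.6% | 7.9-9.9% |
| 2 points | 12.7-17.8% | 29.0-46.4% | 18.5-28.9% |

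For b = 1 in column (a), b/SE is 1/2.49 = 0.40 to 1/1.94 = 0.52. In column (b), λ is 0.90 to 1.48. A 3 d.f. test of differences between arms stays at 5% under (b), because a shift common to all arms cancels.

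**5. Does anything already in the plan mask the reader?** The envelopes do not, since they act only up to assignment. The numeric code does not, since study staff know it and the team holds the link.

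**The case against.** The strongest reply has four parts.

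*The text is silent; it does not say the reader is unmasked.* This stands. The arm-matched meal shows that whoever provides it knows the arm, not that the later reader does. Names are removed, so the reader cannot be identified with the co-investigator who oversees testing. A reader might infer that the tracings are in fact read with knowledge of arm; the documents do not show that.

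*The primary outcome is a sensor quantity.* This largely stands. A reader might infer that percent time pH < 4.0 is itself edited and so biased. The review is tied most directly to episode counts, and an effect on percent time is possible but not established.

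*The assumed shifts have no source, and 0.5 point barely matters.* This stands. It is also tempting to scale an arm-specific shift against the 3.7-point scenario, but that scenario is an equal change in all four arms, with no difference between them. The scenarios that do differ between arms use 4 to 7 points, so 0.5 to 1 point is 0.5/7 = 7% to 1/4 = 25% of those.

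*Full masking is not free.* This stands too. Sections 4.0 and 5.0 exclude participants on the baseline recording at the 5.5% limit, so that tracing must be read promptly and cannot wait for a mixed, visit-masked batch. The existing number would not mask an investigator either. A reader might infer that coding the tracings would remove the problem at no cost; it would not.

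What the reply leaves untouched is that a named Aim 1 outcome is open to judgement by a study investigator in an open-diet trial, with no protection written down.

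**Conclusion.** The point holds in a limited form. As written, the plan leaves reflux-episode counts open to reader bias and leaves it unclear whether percent time pH < 4.0 is open to it as well. The documents do not show that bias will occur, nor its size. If percent time can be altered, average shifts of 0.5 point or less would be of little consequence, while shifts of 1 to 2 points would raise type I error materially, most of all on the 4 d.f. test if the reader knows the visit. Those figures rest on the assumed shifts, the Section 10.0 model and the Section 2.2 inputs under both readings of the SD. No planned sample size, significance level or power figure changes. This is an inexpensive improvement to outcome assessment, not a demonstrated flaw in the primary result. If masking is already practised, stating it in the protocol would settle that part.

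**What to change.** 1. Keep the same reader, but present tracings under a new reading code, separate from the study number, with the key held by someone other than the reader. Mask arm, and lock the reviewed values before unmasking.
2. Read the baseline tracings for eligibility before randomization and lock them then; no arm exists at that point to influence them.
3. Mask visit and date where feasible. Early locking of baseline readings will often make the final tracing recognisable, so full visit masking should not be promised.
4. State in Section 6.0 whether manual correction can change percent time pH < 4.0 or only the episode data.
5. Retain the uncorrected automated values for both outcomes and report them as a sensitivity analysis. This is the main check on any visit-related lean that masking to arm cannot prevent.

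The cost is a small recoding and key-holding task for existing staff. There is no added participant procedure and no change to the sample size. These steps reduce reader bias only; other effects of open diets, such as behaviour during the 24-hour recording, remain.
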